3.4.2 Rationale for Recommended Phase 2 Dose

As of Amendment 4, following review of available safety (refer to Section 3.2.4.1) and PK data, the decision has been made to choose the following as the recommended Phase 2 dose (RP2D) on a Q2W schedule of Sym015 (referenced as the Q2W RP2D):

- Loading dose of 18 mg/kg infused over 1.5 hours on Cycle 1/Day 1 (C1/D1)
- Followed by Q2W maintenance doses of 12 mg/kg infused over 1 hour beginning on Cycle 1/Day 15 (C1/D15)

The rational for this choice is based upon preliminary PK data from the initial 6 mg/kg Q2W (N=3, 2-3 cycles) and 12 mg/kg Q2W (N=3, up to Cycle 2/Day 1) cohorts treated in the dose-escalation phase of this trial. These data were used to establish a population PK model.

The summary PK parameters for these data, based on non-compartmental analysis, are listed in [Table 1](#).

Table 1 Preliminary Sym015 Geometric Mean PK Parameters

Dose Q2W	N	AUC _{0-336h} 1 st dose (h x µg/mL)	C _{max} 1 st dose (µg/mL)	C _{trough} 2 nd dose (µg/mL)	C _{max} 3 rd dose (µg/mL)	t _½ 1 st dose (h)
6 mg/kg	3	19400	146	35.9	196	158
12 mg/kg	3	40000	294	119	396	213 (n=1)

Abbreviations: AUC, area under the concentration-time curve in a dosing interval; C_{max}, maximum concentration; C_{trough}, trough concentration; h, hour; N, number of patients; Q2W, dosing every second week; t_½, elimination half-life

The model was used to simulate average and 90% confidence intervals for Sym015 PK profiles for the 18+12 mg/kg Q2W regimen, and demonstrated that pre-dose serum concentrations, C_{trough}, are likely to be above 100 µg/mL for the vast majority of patients for all dose administrations. The serum concentration of 100 µg/mL has been defined as an approximate threshold for clinical efficacy. This has been deduced from the 750 mg Q2W dose regimen of another anti-MET monoclonal antibody, emibetuzumab, which has shown signs of efficacy in patients with *MET*-amplified tumors ([23,28](#)). It is assumed that similar serum concentrations of Sym015 and emibetuzumab will result in similar clinical efficacy because similar potencies between the two compounds have been observed in preclinical *in vitro* and *in vivo* studies (refer to Investigator's Brochure). *In vivo* studies also support that efficacy can be expected at concentrations above 100 µg/mL for both compounds.

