6.3.1 Withdrawal from Treatment with Sym015

The patient must be withdrawn from treatment with Sym015 in the event of any of the following:

- A DLT considered by the Investigator to require treatment discontinuation. Refer to Section 9.5 for DLT definition (dose-escalation cohorts only)
- Occurrence of an AE considered by the Investigator to require treatment discontinuation
- Basket Cohort ONLY: Results from archival tumor tissue or a tumor biopsy submitted to confirm *MET*-amplification status that do not meet study eligibility criteria.

Note: Such patients may remain on study if there is evidence of an OR, SD, or other clinical benefit, but will not be included in the Evaluable for Response Population.

- PD, verified by CT/MRI according to RECIST v1.1
- Treatment failure not meeting the criteria for PD, but considered by the Investigator to require treatment discontinuation
- Requirement for a significant surgical procedure

Note: Patients requiring a minor surgical procedure (e.g., port placement, skin abscess drainage) may continue at the Investigator's discretion following discussion with the Sponsor or designee. A brief interruption in therapy may be considered

- An intercurrent illness which, in the opinion of the Investigator, would prevent completion of trial-related evaluations
- Use of prohibited concomitant medication, as defined in Section [7.5.2](#)
- Pregnancy
- Significant deviation from the eligibility criteria may require discontinuation after discussion with the Sponsor
- Noncompliance with trial procedures may require discontinuation after discussion with the Sponsor
- Patient withdrawal of consent and election to discontinue treatment. (Patients may leave the trial at any time for any reason if they wish to do so, without any consequences)
- Termination of the trial by the Sponsor
- Patients who meet Hy's Law criteria that cannot be explained by factors not related to Sym015.

Note: Patients meeting all three of the following are considered to have met Hy's Law criteria:

- The drug causes hepatocellular injury, generally shown by a higher incidence of 3-fold or greater elevations above ULN of ALT or AST
- Among trial subjects showing such aminotransferase elevations, often much greater than 3xULN, one or more show elevation of serum total bilirubin to ≥ 2 xULN, without initial findings of cholestasis (elevated serum alkaline phosphatase [ALP]).

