7.1.4.2 Dose-Delays for Sym015-Related or Disease-Related Toxicities

Clinical judgment will be used when determining whether it is advisable to continue a patient on to the next dosing. In order to dose a patient, the following criteria must be met:

- ANC $> 1.0 \times 10^9/L$ (1000/mm³)
- Platelet count $> 60 \times 10^9/L$ (60,000/mm³)
- Any ongoing AEs should NOT meet the criteria for DLT, during the DLT observation period
- Any ongoing AEs, assessed as possibly, probably, or related to Sym015, should have either ameliorated to \leq Grade 1 severity, returned to baseline status, or resolved with the exception of Grade 2 clinical events that are being adequately controlled with best supportive care (e.g., nausea, vomiting, diarrhea, fatigue) and asymptomatic laboratory abnormalities that are considered clinically insignificant or that are resolving with medical therapy

Should any one of the criteria above not be met, dosing of Sym015 must be delayed until the patient meets the above criteria. All per protocol assessments must be done.

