7.1.4.3 Dose-Reduction for Sym015-Related Toxicities

Patients experiencing any of the following toxicities, assessed as possibly, probably, or related to Sym015, will have their dose reduced in accordance with the reduction schedule outlined in [Table 7](#).

1. Grade 3 non-hematologic toxicity regardless of duration, with the exceptions of:
 - a. Grade 3 nausea, vomiting, diarrhea, or fatigue lasting \leq 2 days with best supportive care
 - b. Grade 3 asymptomatic electrolyte abnormalities lasting \leq 3 days that are not considered clinically relevant by the Investigator and that resolve with medical therapy without requiring hospitalization
2. Any Grade 4 non-hematologic toxicity, with the exception of:
 - a. Grade 4 asymptomatic electrolyte abnormalities lasting \leq 3 days that are not considered clinically relevant by the Investigator and that resolve with medical therapy
3. Neutropenia that is:
 - a. Grade 3-4 febrile neutropenia
 - b. Grade 4 and sustained (i.e., ANC <500 per mm 3 , duration >5 days)
4. Thrombocytopenia that is:
 - a. Grade 3 with clinically significant hemorrhage
 - b. Grade 4 (platelets $<25,000$ per mm 3)
5. AST/ALT elevation $>3\times$ ULN with bilirubin elevation $>2\times$ ULN that cannot be explained by factors not related to study drug

Table 7 Sym015 Dose-Reduction Schedule

Allocated Dose	First Reduction	Second Reduction	Subsequent Reductions
6 mg/kg	3 mg/kg	1.5 mg/kg	Reduce by 50%
12 mg/kg	6 mg/kg	3 mg/kg	Reduce by 50%
18 mg/kg	12 mg/kg	6 mg/kg	Reduce by 50%
24 mg/kg	18 mg/kg	12 mg/kg	Reduce to 6 mg/kg, then by 50%

Note: In the event that an intermediate dose is explored in this study, dose-reductions in such cases will be to the next lower established tolerated dose level(s). If further dose-reductions are indicated, proceed as outlined above.

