8.2.9.2 Biochemistry Panel

To include sodium, potassium, chloride, bicarbonate or carbon dioxide, blood urea nitrogen (BUN), creatinine, glucose, bilirubin [total and direct], AST, ALT, ALP, calcium, magnesium, phosphorus, albumin, total protein, uric acid, amylase, lipase, and creatine kinase (fasting not required). Clinically significant electrolyte abnormalities should be corrected prior to dosing.

- Screening
- Cycle 1
 - Weekly (prior to Sym015 administration on days of dosing)
 - Does not need to be performed prior to C1/D1 if performed during screening ≤ 7 days from C1/D1
 - Day 3
- Each cycle thereafter
 - Prior to each dosing
- EOT

- 1M FUP
- As clinically indicated

In the event of significant biochemistry abnormalities, the evaluation frequency should be increased to include additional evaluations between the scheduled assessments, as clinically indicated. In the event of creatine kinase abnormalities, isoenzyme analysis should be performed.

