9.1.4 Serious Adverse Events

An SAE is an AE that meets one or more of the following outcome criteria:

- Results in death

Note: In the case of deaths, the event(s) leading to the death should be recorded and reported as SAE(s) with the outcome "Fatal". The death itself will not be reported as an event (SAE), unless the cause of the death is unknown (e.g., in case of unexplained or sudden death)

- Is life-threatening

Note: The term "life-threatening" in this definition refers to an event in which the patient is at immediate risk of death at the time of the event; it does not refer to an event which hypothetically might cause death if it was more severe

- Requires inpatient hospitalization or prolongation of existing hospitalization
- Results in persistent or significant disability/incapacity
- Is a congenital anomaly/birth defect
- Is medically important

Note: Medical and scientific judgment must be exercised in deciding whether an AE is believed to be "medically important". Medically important events may not be immediately life-threatening or result in death or hospitalization but may jeopardize the patient or may require intervention to prevent one of the other outcomes listed in the definition above

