9.5 Dose-Limiting Toxicities (Part 1 Only)

9.5.1 Definition of Dose-Limiting Toxicities

A DLT is defined as any of the following toxicities that occur during the DLT observation period, if considered related (causality rating of possibly, probably, or related) to Sym015:

1. Grade 3 non-hematologic toxicity regardless of duration, with the exceptions of:
 - a. Grade 3 nausea, vomiting, diarrhea, or fatigue lasting \leq 2 days with best supportive care
 - b. Grade 3 asymptomatic electrolyte abnormalities lasting \leq 3 days that are not considered clinically relevant by the Investigator and that resolve with medical therapy
2. Any Grade 4 non-hematologic toxicity, with the exception of:
 - a. Grade 4 asymptomatic electrolyte abnormalities lasting \leq 3 days that are not considered clinically relevant by the Investigator and that resolve with medical therapy.
3. Neutropenia that is:
 - a. Grade 3-4 febrile neutropenia
 - b. Grade 4 and sustained (i.e., ANC <500 per mm³, duration >5 days)
4. Thrombocytopenia that is:
 - a. Grade 3 with clinically significant hemorrhage
 - b. Grade 4 (platelets $<25,000$ per mm³)
5. AST/ALT elevation $>3\times$ ULN with bilirubin elevation $>2\times$ ULN that cannot be explained by factors not related to study drug
6. Inability to complete Cycle 1 at the assigned dose due to \geq Grade 3 toxicity

7. Treatment delays >2 weeks from the scheduled “next dose” due to \geq Grade 3 toxicity

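### Section 7.1.4.3 requires a dose reduction for a hospitalized, otherwise exempt electrolyte abnormality at Grade 3 but not for the same event at Grade 4

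*Protocol*

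**What the plan says.** Protocol section 7.1.4.3 lists toxicities that, if at least possibly related to Sym015, lead to a dose reduction under Table 7. The wording is mandatory. Item 1 covers Grade 3 non-hematologic toxicity and item 2 covers Grade 4. Each has an exception for asymptomatic electrolyte abnormalities lasting 3 days or less.

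- Item 1b (Grade 3) exempts those "that are not considered clinically relevant by the Investigator and that resolve with medical therapy without requiring hospitalization".
- Item 2a (Grade 4) begins "Grade 4 asymptomatic electrolyte abnormalities lasting" and repeats the duration limit, the relevance judgment and resolution with medical therapy. It ends there, with no mention of hospitalization.

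The dose-limiting toxicity definition in section 9.5.1 has parallel items 1b and 2a. Both exempt abnormalities "that are not considered clinically relevant by the Investigator and that resolve with medical therapy", and neither adds a hospitalization condition.

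**The concern.** A mandatory safety rule should not become more lenient as the grade rises. Here the extra condition sits only on the Grade 3 exemption. A patient admitted for a brief, symptom-free Grade 3 abnormality must be reduced, while a patient admitted for the Grade 4 equivalent may stay on full dose. At stake is the coherence of the reduction rule and the dose given to the rare patient who falls in the gap. Nothing inferential depends on it.

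**Working it through.** The protocol gives no rate for such events, so the check is a comparison of the two exemptions on one test case: a Sym015-related electrolyte abnormality that meets every shared condition but requires hospitalization.

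| Condition | Item 1b (Grade 3) | Item 2a (Grade 4) | Test case |
|---|---|---|---|
| Asymptomatic | required | required | met |
| 3 days or less | required | required | met |
| Judged not clinically relevant | required | required | met |
| Resolves with medical therapy | required | required | met |
| No hospitalization needed | required | absent | not met |
| Result | exemption fails: reduce | exemption holds: no reduction required | |

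Next, does any other section restore a required reduction at Grade 4?

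- Section 8.2.9.2: "Clinically significant electrolyte abnormalities should be corrected prior to dosing". This concerns correction before dosing, and only of significant abnormalities. The test case is by construction judged not relevant.
- Section 7.1.4.2 governs delay. It allows dosing to go ahead with "asymptomatic laboratory abnormalities that are considered clinically insignificant or that are resolving with medical therapy".
- Section 6.3.1 requires withdrawal on "Occurrence of an AE considered by the Investigator to require treatment discontinuation", which rests on the investigator's judgment.

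None of the three imposes a Grade 4 reduction. Section 9.5.1 treats the two grades alike, so the inversion is confined to 7.1.4.3.

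The dose consequence of a reduction in Part 2 can be given only as a range. The regimen in section 3.4.2 is an 18 mg/kg loading dose, "Followed by Q2W maintenance doses of 12 mg/kg infused over 1 hour", and Table 7 has no row for that combination. Measured against planned maintenance of 12 mg/kg:

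- First reduction, 12 mg/kg row: to 6 mg/kg; (12 − 6)/12 = 50% lower.
- First reduction, 18 mg/kg row (event after the loading dose): to 12 mg/kg; (12 − 12)/12 = 0% lower.
- Second reduction, 12 mg/kg row: to 3 mg/kg; (12 − 3)/12 = 75% lower.

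As things stand, the Grade 3 patient in the test case bears one of these reductions and the Grade 4 patient bears none.

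**The case against.** The strongest objection is that almost nobody falls in the gap. Admission is itself a seriousness criterion in section 9.1.4: "Requires inpatient hospitalization or prolongation of existing hospitalization". The investigator would have to call the event related, Grade 4 and serious, yet asymptomatic and not clinically relevant. In most admitted cases the relevance condition in 2a already fails, and the dose is reduced at both grades. That stands, and it is why the point is small. It does not make the case empty. Item 1b lists hospitalization in addition to clinical relevance, so the protocol treats them as separate conditions. Section 9.1.2 likewise lists clinical significance and meeting the serious-event definition as separate grounds for reporting a laboratory value.

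A second objection is that the gap closes by itself. Section 9.2.3 asks for changes in severity to be recorded, so a Grade 4 abnormality that passes through Grade 3 while resolving in an admitted patient might be read as triggering item 1. This reading is possible, but the text does not state it. A value that falls from Grade 4 to Grade 2 between samples would escape it.

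A third objection is that item 2a matches 9.5.1 on purpose. The amendment summary says that Amendment 4 aligned dose-reduction criterion 2 with the dose-limiting toxicity criteria. That is true, but Amendment 1 had added the hospitalization condition to 1b just as deliberately. The protocol does not say which should give way, and it offers no reason for leniency at Grade 4.

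The safeguards on correction, delay and withdrawal also make actual harm from this wording unlikely.

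**Conclusion.** The inversion is in the current text: for the test case, reduction is compulsory at Grade 3 and not required at Grade 4. This is a minor drafting fault in a safety rule. It rests on reading items 1b and 2a as written, and on the investigator having judged an admitted event not clinically relevant.

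A reader might infer three stronger things that the documents do not support.

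- That the rule is self-contradictory and cannot be followed. Each item can be applied without ambiguity; only the ordering of the grades is wrong.
- That dose escalation or the choice of Part 2 dose is compromised. Section 9.5.1 is symmetric, and no effect on the primary endpoint, analysis or sample size follows.
- That the exposure figures in Table 1 measure harm from this wording. They compare the 6 and 12 mg/kg cohorts, with three patients each, and say nothing about how often, or to what effect, the Grade 4 exemption would be used.

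**What to change.** Add to the end of item 2a in section 7.1.4.3 the same no-hospitalization condition that closes item 1b. This keeps the existing Grade 3 safeguard and ensures that Grade 4 is never treated more leniently. Deleting the condition from 1b would also remove the inversion and would match 9.5.1, but it gives up that safeguard.

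The cost is one phrase at the next amendment. No new data are needed, because inpatient hospitalization is already captured for serious-event reporting. The downside is an occasional extra reduction for a Grade 4 patient, of the sizes worked out above. Item 2a would also then differ from its counterpart in 9.5.1, as item 1b already does.

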7.2 Other Drugs to be Used in the Trial

7.2.1 Premedication for Sym015 Infusions

There is an inherent risk for IRRs with the administration of mAbs. A premedication schedule will therefore be implemented for all patients treated.

For Part 1 of the trial, premedication is mandatory prior to each dose of Sym015.

For Part 2 of the trial, premedication is mandatory prior to each dose of Sym015 during Cycle 1.

All patients must be premedicated as described with standard therapies that include a glucocorticoid and an H1 antagonist. Where indicated, consideration may be given to including an H2 antagonist and/or acetaminophen. The recommended premedication doses are as follows:

- Glucocorticoid therapy equivalent to 80-100 mg IV methylprednisolone, approx. 0.5 to 2 hours prior to the start of Sym015 infusion
- Antihistamine (H1 antagonist) equivalent to 25-50 mg IV diphenhydramine, approx. 0.5 hours prior to the start of Sym015 infusion
- Antihistamine (H2) antagonist (optional) such as 50 mg IV ranitidine or 30 mg famotidine, approx. 0.5 hours prior to the start of Sym015 infusion
- Acetaminophen (optional) such as 1000 mg IV or PO (orally), approx. 0.5 hours prior to the start of Sym015 infusion

In Part 2, if a patient is without evidence of IRRs after Cycle 1, the Investigator may opt to withdraw premedication on a patient-by-patient basis with subsequent dosing in order to determine whether such continued therapy is necessary in that patient. Where practical, it is recommended that withdrawal of premedication be done in a gradual fashion.

For those patients who experienced symptoms suggestive of an IRR after Cycle 1, consideration should be given to continuing premedication for at minimum 1 to 2 additional doses before any future attempt to withdraw.

7.2.2 Prophylactic and Therapeutic Treatment

7.2.2.1 Mandatory Prophylactic Treatment

Mandatory prophylactic treatment will be implemented for all patients treated in this trial should an increased incidence begin to occur of mild-to-moderate Sym015-related reactions that are amenable to prophylaxis with standard agents. Such actions will occur following discussions within the SMC.

7.3 Blinding

Not applicable as this is an open-label trial.

7.4 Drug Accountability and Compliance Check

The Investigator is responsible for ensuring accountability for the IMP, including maintenance of IMP accountability records.

IMP accountability records will include a full inventory of the IMP including:

- Confirmation of IMP delivery to the trial site
- Record of each dose dispensed
- The return of unused IMP to the Sponsor or designee
- Record of any on-site destruction of unused IMP, as agreed with the Sponsor or designee

Records will specify dates, quantities, batch numbers, use-by dates and patient numbers, as applicable.

The Investigator, or designee, should maintain records that adequately document:

- That the patients were provided the doses specified by the protocol, and
- That all IMP provided by the Sponsor was fully reconciled

7.5 Concomitant Medication/Therapy

7.5.1 Allowed Medication/Therapy and Procedures During the Trial

Patients may receive their current concomitant medication and any medication considered necessary for the welfare of the patient during trial, except if listed in Section [7.5.2](#).

Furthermore, the following are permitted during the trial:

- Premedication with standard therapies prior to Sym015 administration to reduce the risk of IRRs
- Prophylaxis and treatment of Sym015-related toxicities
- Radiotherapy for pain control against non-target lesions, as long as it does not influence bone marrow function
- Bisphosphonates and denosumab: Bisphosphonates and denosumab for bone metastases and other skeletal conditions provided the patient is on a stable dose for at least 2 months prior to study start and remains on the stable dose while receiving study treatment

7.5.2 Prohibited Medication/Therapy and Procedures During the Trial

The following medications and procedures are not allowed from C1/D1, or as specified in the inclusion/exclusion criteria, until the EOT Visit:

- Anti-cancer treatment, including cytotoxic or cytostatic agents, hormonal therapy (except as physiologic hormone replacement)

- Basket Cohort ONLY: MET-targeting therapies, except in subset of approximately 6 patients
- Radiotherapy against target lesion(s) (Part 2 only)
- Systemic immunosuppressive or systemic hormonal therapy with the exception of the following allowed therapies:
 - Hormonal therapy (e.g., Megace) for appetite stimulation
 - Nasal, ophthalmic, inhaled, and topical glucocorticoid preparations
 - Oral replacement glucocorticoid therapy for adrenal insufficiency
 - Low-dose maintenance steroid therapy for other conditions (excluding steroid tapers for brain edema/metastases/radiation)
 - Steroid therapy as prophylaxis for contrast reactions
 - Stable hormonal therapy for ovarian suppression for non-malignant conditions, hormonal contraceptive therapy, or post-menopausal HRT*
 - GnRH analogs in patients with prostate cancer
 - Intra-articular steroid injections
 - Higher dose steroid therapy for treatment of an acute intercurrent illness in patients with stable disease or an ongoing response. In such situations, protocol therapy treatment should be interrupted.

*Prior or concomitant therapies are permitted; however, patients must have been on a stable dose for at least 6 months prior to study start, and if continuing must remain on the stable dose while receiving study treatment (i.e., such treatment will not be considered as systemic hormonal therapy for the purpose of study eligibility).

- Prophylactic use of hematopoietic growth factors during Cycle 1
- Major surgery that would preclude the patient from complying with the requirements of the protocol

If any one of the above listed medications/procedures becomes necessary during the trial, the patient must be withdrawn from Sym015 and the EOT Visit should be performed. The 1M FUP Visit should then be performed, no less than 1 month (30 +7 days) after the last dose of Sym015.

